5.2 Informed consent

Signed informed consent will be obtained from each subject. The informed consent process will follow the procedures of the WFU Institutional Review Board. The study team member will explain the purpose, methods and extent of the study to prospective participants. The potential participant is asked to read the informed consent form and ask questions. The form is written in simple, easy to understand language. We require study staff to review all of the key aspects of the study verbally with the potential participants. The staff will be provided with a structured checklist for this purpose. The study staff will question potential participants to ascertain whether s/he has understood the information. Potential participants who are illiterate or have impaired vision must have the consent read to them, followed by review of the checklist, opportunity for questions, and discussion. This process will take place in the patient's private room in 9cc of Wake Forest Baptist Health. For providers, the process will take place in the conference or workroom on 9cc of Wake Forest Baptist Health. A copy of the signed and dated consent form will be given to participants, and the original document will be placed in subjects' individual study files, which will be stored in a secure location. In compliance with the Health Insurance Portability and Accountability Act (HIPAA) and the Standards for Privacy of Individually Identifiable Health Information of the Department of Health and Human Services, we will access personal health information only after obtaining informed consent.

Feasibility Assessment of the Wake Forest Real-time Tracking System for Monitoring
Patient Movement during Postoperative Recovery: Part 2
IRB 00039439

5.3 Pedometer and Step Data

The Fitbit Zip™ (Fitbit Inc., San Francisco, CA; www.fitbit.com) is a lightweight, portable pedometer device that contains a tri-axial accelerometer. The device is commercially available to consumers and is considered a recreational device. It is capable of tracking multiple measures of physical activity including steps and distance traveled. Tracking data is stored on the device for several weeks and is capable of being downloaded to a computer for analysis using USB or wireless connection. The accuracy of the Fitbit One™ and Fitbit Ultra™ have been independently validated.^{15,16} The Fitbit device can be worn on various body locations (hip vs. pocket) and maintains a high level of accuracy.¹⁶

The Kenz Lifecorder EX Accelerometer is an accurate and reliable research grade activity monitor that, in addition to counting steps, calculates calories expended, monitors the intensity and duration of physical activity, computes basal metabolic rate (BMR) and stores 200 days of data. Each participant's height, weight, age, gender, as well as the time of day will be programmed into the device before given to the participant.

Each participant will wear the pedometer devices during their daily walk with research staff. Programming of the Fitbit Zip™ and Kenz Lifecorder EX Accelerometer will be performed by research staff.

The pedometer data will be stored in a secure, password-protected file behind the WFBH firewall.

5.4 Patient Medical Record Review

All participants will have medical records reviewed to determine specific details regarding their medical condition, diagnosis, co-morbidities, laboratory data (nutritional status), medications, social history, past operations, and operation. If barriers to successfully completing the study are identified, the participant may be dismissed from the study. Relevant clinical data will be collected and stored in RedCap.

5.5 SPOT/RTLS Badges and Data

All participants will wear a SPOT badge provided by the study team throughout the study period. Research staff will stress that participants should wear the pedometer during the study period. Participants will be asked to wear the activity monitors at all times except while bathing or showering. SPOT badge data is collected continuously by the SPOT team independent of the study team. This is standard procedures for Wake Forest Baptist Health. The study team will coordinate with the SPOT team to extract data specific for this study. The extracted data will be stored in secure, password-protect files behind the WFBH firewall using excel files.

5.6 Walking Assessment and Physical Activity Survey (Observational Cohort)

All participants will receive a visit by a study team member each day for maximum of 3 days. If discharge is less than 24 hours after enrollment, the participant will be excluded from study. Study participants will be invited by a study team member to join them on a walk. Time, distance, and duration will be determined by the patient. If nursing staff or treating provider determines that walking is not safe or inappropriate, walk will not be performed and rationale documented. If patient declines to walk, rationale will be documented. For all patients who decline, a second visit by a study team member will occur later in the day. Participants will be encouraged to walk by study team members emphasizing the importance of walking after surgery. Each participant will complete a pre- and post-walk assessment including measurement of pain and fatigue. Pre- and post-walk vital signs will be recorded. Participants will also be asked to report number of walks completed in the last 24 hours along with distance traveled. At completion of walk, the study team will record exact time of walk, distance, and duration. At conclusion of walk assessment, the patient will complete a physical activity in hospital survey. Survey data will be collected in the subject's private room.

5.7 HIIT Cohort

5.7.1 Physical Activity Survey

Prior to the ambulatory session, the subject will receive information regarding the type of exercise they will be engaging in (continuous or HIIT). The subject will also complete a questionnaire regarding their current level of physical fitness to determine his/her qualitative baseline.

5.7.2 Vital signs

The subject's heart rate, blood pressure, pulse, and respiratory rate will be collected before and after each ambulatory session.

5.7.3 Grip Strength

Grip strength will be measured as a baseline. Two trials will be measured and then averaged together for the right and left arm. This will provide a baseline objective measure of subject frailty.

5.7.4 Ambulatory Session

Each subject perform one ambulatory session during the study. This will include walking 40 meters. Gait speed will be calculated using the speed

Feasibility Assessment of the Wake Forest Real-time Tracking System for Monitoring Patient Movement during Postoperative Recovery: Part 2
IRB 00039439

in which the subject walked 40 meters. Alternative exercise (hand bike) will be provided if subject declines ambulation or unable to ambulate out of their room. Demonstration of the hand bike will be provided by the study team member and subjects will be allowed to practice with the bike prior to exercise session. For subjects unable to perform the ambulatory session, a study team member will return on a subsequent hospital day to complete this portion of the study. If patient unable to perform the ambulatory session during their hospitalization or during the study period, the reason will be documented.

1. Walking Continuous Training (Group 1): The total distance will be 40 meters. Study team members will walk, support, and coach the subject to walk as slow as he/she wants.
2. Walking Interval Training (Group 2): The subject will walk a total distance of 40 meters. This distance will be divided into four intervals of 10 meters to equal the same measured distance as the continuous group. The subject will receive two minutes of rest between each interval and will be supported and coached to walk as fast as they can.
3. Hand Bike Continuous Training (Group 1, alternative option until able to participate in ambulatory session): The subject will be asked to bike for 5 minutes continuously with coaching “go as slow as you want.”
4. Hand Bike Interval Training (Group 2, alternative option until able to participate in ambulatory session): The subject will be asked to bike in 10 second intervals (“as fast as they want to go”) and rest for 50 seconds for five rounds (i.e. every minute on the minute (EMOM)).

5.7.5 Perceived Exertion

Subject perceived exertion will be evaluated at the beginning, at 20 meters, and at the end of the ambulatory session using a standard RPE scale.

5.7.6 Gait Speed

Gait speed (meters/second) will be calculated at the end of each session based on distance traveled over time.

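### Does the plan need to state that the interval group's two-minute rests are left out of gait speed?

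*Combined protocol and SAP*

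**What the plan says.** Gait speed in the HIIT cohort is described in two places in the combined protocol and SAP.

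- Section 5.7.6 gives the formula and the moment of calculation: "Gait speed (meters/second) will be calculated at the end of each session based on distance traveled over time".
- Section 5.7.4 has a sentence that a page break splits in two. It begins "Gait speed will be calculated using the speed" and ends "in which the subject walked 40 meters".

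Section 5.7.4 also sets out the two walking patterns. For the continuous group: "Walking Continuous Training (Group 1): The total distance will be 40 meters", with no scheduled rest. For the interval group: "This distance will be divided into four intervals of 10 meters to equal the same measured distance as the continuous group", and then "The subject will receive two minutes of rest between each interval and will be supported and coached to walk as fast as they can".

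The only explicit instruction to time a walk is in section 5.6, for the observational cohort: "At completion of walk, the study team will record exact time of walk, distance, and duration". Section 5.0 states that this cohort is closed to enrollment. The same section says that examiners are trained in standardized conduct of all assessments before data collection, and that standardized written instructions will be provided.

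**The concern.** Neither section says that the rests are excluded, that each 10 m interval is timed, or that a stopwatch is paused. An assessor could read section 5.7.6 alone, start a watch at the first step, stop it at the end of the session, and divide 40 m by the result. For Group 1 that gives the walking speed. For Group 2 it gives a number made up mostly of rest.

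The group coached to walk fast would then appear slower than any Group 1 patient moving above 0.111 m/s, and differences among Group 2 patients would almost vanish. With at most 10 patients planned in that group, a few sessions timed differently from the rest would distort its summary. If only the session total had been kept, the walking time could not be recovered exactly afterwards. This is why the point looks like something to settle before data collection.

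**Working it through.** The documents state no gait-speed figure, so there is none to reproduce. The check compares the two possible denominators.

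**Inputs from section 5.7.4**
- Distance in Group 2: 4 × 10 m = 40 m, the same as Group 1.
- Rests fall between four intervals, so there are 4 − 1 = 3.
- Total rest: 3 × 120 s = 360 s.

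**Assumed input**
- True walking speed *v*. The documents give none, so a range is shown.

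**Formulas**
- Walking time: speed = 40 / (40/*v*) = *v*. No error.
- Elapsed session time: speed = 40 / (40/*v* + 360).
- Ratio of the two: *v* × (40/*v* + 360) / 40 = 1 + 9*v*.
- Ceiling on elapsed time as *v* grows: 40/360 = 0.111 m/s.

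| Assumed *v* (m/s) | Walking time (s) | Elapsed time (s) | Speed on elapsed time (m/s) | Ratio |
|---|---|---|---|---|
| 0.4 | 100.0 | 460.0 | 0.087 | 4.6 |
| 0.8 | 50.0 | 410.0 | 0.098 | 8.2 |
| 1.0 | 40.0 | 400.0 | 0.100 | 10.0 |
| 1.5 | 26.7 | 386.7 | 0.103 | 14.5 |

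The two readings are therefore far apart, and the question is which one the text supports.

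**Reading the sections together**
1. Section 5.7.6 supplies a generic formula. Its reference to the end of the session says when the calculation is made, not what the denominator is.
2. Section 5.7.4 supplies the content: the speed at which the 40 m was walked. A patient who is resting is not walking.
3. Section 5.7.4 divides the distance so that both groups cover the same measured length. That points to an intention to keep the groups comparable, which elapsed time would defeat.
4. An instruction to compute metres per second over a fixed 40 m already implies that a time is recorded. Timing each interval and adding, or pausing one watch during rests, gives the same denominator.
5. Section 5.6 needs its explicit recording instruction because there the patient chooses time, distance and duration. The lack of a matching sentence in section 5.7 is weak evidence that timing was overlooked.

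**Where gait speed is used**
- Section 6 does not list it among the outcomes.
- Section 7.2 does not mention it, and makes the analysis descriptive.
- The 80% criterion in section 7.2 concerns badges detecting movement in and out of a room.
- Aim 3.2.2 mentions speed, but for characterizing daily movement rather than for comparing the HIIT groups.

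**The case for a change.** The strongest argument for a change is that it costs almost nothing and the error, once made, is hard to undo. One sentence in section 5.7.6 and four time fields on the form would remove the ambiguity. Gait speed also has its own subsection, and it is the direct measure of the pace that the two coaching styles are meant to vary. Anyone describing tolerance of the two intensities (aim 3.2.6, outcome 6.2.7) would naturally turn to it, even though the documents do not make that link.

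The repair problem can be put in numbers. Suppose only the session total was kept and a nominal 360 s was subtracted. If each rest missed by an assumed 5 s in the same direction, a true 1.0 m/s would come out between 40/55 = 0.73 and 40/25 = 1.60 m/s. That is a worst case. If the three deviations were independent, the typical combined deviation would be √3 × 5 = 8.7 s, giving about 40/48.7 = 0.82 to 40/31.3 = 1.28 m/s. Nothing in the documents suggests that staff would work this way.

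What stands is that the rule is not written in the documents, and that the promised instructions cannot be inspected to see whether they contain it. What does not stand is the inference that staff would be left to choose, or would choose elapsed time. A systematic slip would also show itself at once: every Group 2 value would lie below 0.111 m/s in patients coached to walk fast.

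**Conclusion.** No change to the plan is called for. Sections 5.7.4 and 5.7.6 leave the denominator unstated, but read together they point to walking time, and on that reading the error is zero in both groups. The large distortion (4.6-fold at an assumed 0.4 m/s, 14.5-fold at 1.5 m/s) arises only if elapsed session time is used, against the sense of section 5.7.4.

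Even then it would touch at most the 10 planned Group 2 patients, on a descriptive variable that no listed outcome or feasibility criterion names. Writing the definition into section 5.7.6 would be harmless, but it would only record what a trained assessor would be expected to do.

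The conclusion rests on two assumptions: that section 5.7.4 governs the meaning of section 5.7.6, and that the training and written instructions promised in section 5.0 cover the timing of a walk that includes scheduled rests.

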5.8 Provider Physical Activity Survey

All provider participants will complete a physical activity survey and repeat the survey after 30 days of providing care for patients on 9cc. During the study period, patient mobility data will be available to providers.

6.0 Outcome Measures

- 6.1 Primary Outcome: Determine if the SPOT system can detect movement in and out of a patient's room.
- 6.2 Secondary Outcomes:
 - 6.2.1 Characterize patterns of patient movement after surgery.
 - 6.2.2 Characterize number of times of patient exits a room per day after surgery.
 - 6.2.3 Characterize distances traveled per time out of room per day after surgery.
 - 6.2.4 Characterize patient opinion regarding exercise after surgery.
 - 6.2.5 Characterize provider opinion regarding in-hospital exercise programs, monitoring patient movement, and reporting patient movement.
 - 6.2.6 Determine if the SPOT system can detect movement when a patient varies their ambulatory behavior.
 - 6.2.7 Characterize patient's ability to tolerate various ambulatory intensities after surgery.
 - 6.2.8 Describe patient readiness for discharge.

7.0 Analytic Plan

7.1 Sample size

40 subjects will be included in initial observational study. Preliminary tests of SPOT badges indicate sensitivity and specificity nearly 100% using controlled movements on 9cc. Assuming type I error of 0.05, a two-sided test, 20 subjects, the sensitivity or specificity under the null equal to 0, and prevalence of 0.3, we have more than 90% power to detect the sensitivity of specificity under the alternative hypothesis equal to 0.9. If we use a range of prevalence from 0.1 to 0.9, we still have more than 90% power. However, the positioning of SPOT badge may decrease the sensitivity and specificity of the movement readings. Review of preliminary survey data indicates significant variability in response indicating need for expansion of sample size for secondary study objectives. With 40 subjects being recruited, we will be sure to have enough power to demonstrate the feasibility of this study and provide appropriate confidence intervals for future studies.

For provider participants, a maximum of 50 respondents will be included in the study. Based on staffing, resource demands, and learner rotations, the exact number of respondents available may be lower than 50 respondents. With 50 subjects being recruited, we will be sure to have

Feasibility Assessment of the Wake Forest Real-time Tracking System for Monitoring Patient Movement during Postoperative Recovery: Part 2
IRB 00039439

enough power to demonstrate the feasibility of exercise and patient mobility monitoring programs. This number will also provide appropriate confidence intervals for future studies.

For the additional HITT cohort, we will enroll a maximum of 22 subjects. This sample size will have sufficient power to demonstrate the feasibility of this study and provide appropriate confidence intervals for future studies.

In total, targeted study enrollment will be 62 patients and 50 providers.

7.2 Feasibility analysis and statistics.

The study team will also capture information from this pilot study that will be used to improve the efficiency of larger studies. We will evaluate the capabilities of the SPOT system to monitor patient movement. Feasible study will be defined as more than 80% of badges assigned to the observational study participants will detect movement in and out a room. All data will be descriptive in nature and will focus on patterns of movement and presence or absence of data. Summary statistics such as means and standard deviations will be calculated for continuous measures and counts and percentages will be calculated for discrete measures. Agreement statistics, including kappa statistics, sensitivity, and specificity, will be calculated. Changes of pre- and post- vital signs will be calculated and graphical display will be performed to show the changes over time. The correlation between walking distance as well as pain and fatigue will be calculated each day. Mixed effects models will be used to study the association over time. Since the sample size is small, we are aware that the models may not be stable. Thus, descriptive analysis will be our primary analysis.

The additional HITT study cohort will enable validation of SPOT system to capture out of room events under various ambulatory patterns. This will build on the current cohort that validated simple in and out of room events. Feasible study will be defined as more than 80% of badges assigned to participants detect movement in and out a room during continuous and interval movement patterns.

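### Section 7.1's only power calculation tests against a null of 0, so it does not support the claims of enough power to demonstrate feasibility under the >80% badge criterion

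*Combined protocol and SAP*

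**What the plan says.** Section 7.1 gives one calculation: two-sided type I error 0.05, 20 subjects, alternative sensitivity or specificity 0.9, and "the sensitivity or specificity under the null equal to 0, and prevalence of 0.3, we have more than 90% power". It adds: "If we use a range of prevalence from 0.1 to 0.9, we still have more than 90% power".

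It then moves to 40 patients for two reasons. Badge positioning may lower performance, and "Review of preliminary survey data indicates significant variability in response indicating need for expansion of sample size for secondary study objectives". No figure follows. Three assertions are made:

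- Observational cohort: "With 40 subjects being recruited, we will be sure to have enough power to demonstrate the feasibility of this study".
- Providers (at most 50, possibly fewer): "With 50 subjects being recruited, we will be sure to have" "enough power to demonstrate the feasibility of exercise and patient mobility monitoring programs".
- HIIT cohort (at most 22): "This sample size will have sufficient power to demonstrate the feasibility of this study and provide appropriate confidence intervals for future studies".

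Confidence intervals are promised for all three groups, with no width for any.

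Section 7.2 defines feasibility for the first cohort as "more than 80% of badges assigned to the observational study participants will detect movement in and out a room". For HIIT it sets the same threshold, for badges assigned to participants, across continuous and interval movement. It makes the descriptive analysis primary. No feasibility criterion is given for providers. Section 5.0 closes the observational cohort to enrolment and splits HIIT into 12 continuous and 10 interval patients. Section 5.7.4 gives each patient one session.

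**The concern.** A sample-size section should bear on the criterion by which the study will be judged. Here the criterion is a detection rate above 80%, while the calculation asks only whether sensitivity or specificity differs from 0. A badge system that misses most movements would pass that test. A reader who takes the power sentences at face value will believe that a feasible result in 40 or 22 patients establishes a rate above 80%, and may size later studies on that belief.

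The HIIT cohort matters most, because it is the only patient cohort still enrolling. No patient walks in both patterns, so its criterion could be one proportion over 22 badges or a requirement on each group of 12 and 10.

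**Working it through.** **Inputs.** From section 7.1: n=20, two-sided 0.05, null 0, alternative 0.9, prevalence 0.3 (range 0.1 to 0.9). From sections 5.0, 7.1 and 7.2: group sizes 40, 22, 12 and 10, and the threshold of more than 80%. Assumptions: one independent result per patient, and all patients evaluable. The documents give no true per-badge rate in patients, so 0.80, 0.90, 0.95 and 0.99 are used where shown; 0.99 stands in for the near-100% performance in controlled tests.

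**1. The plan's own figure.** With a null of 0, any detection rejects. With *m* positives and sensitivity *s*, power is 1 − (1 − *s*)^m.

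- Prevalence 0.3, m = 20 × 0.3 = 6: 1 − 0.1^6 = 0.999999.
- Prevalence 0.1, m = 2: 1 − 0.1^2 = 0.99. Specificity at prevalence 0.9 is the same.

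The claim of more than 90% reproduces. But with m = 6 and s = 0.32, power is 1 − 0.68^6 = 0.90, so the test hardly separates a good system from a poor one. A null of 0.5, in case 0 is a misprint, gives 53% (m = 6) and 84% (m = 14), not above 90%.

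**2. The >80% criterion as a descriptive rule.** The chance of meeting it is P(X ≥ r), with X binomial and r the smallest count above 80%.

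| Group | r | true 0.80 | true 0.90 | true 0.95 |
|---|---|---|---|---|
| n=40 | 33 | 0.44 | 0.96 | 0.999 |
| n=22 pooled | 18 | 0.54 | 0.94 | 0.996 |
| n=12 | 10 | 0.56 | 0.89 | 0.98 |
| n=10 | 9 | 0.38 | 0.74 | 0.91 |
| both patterns (product) | 10 and 9 | 0.21 | 0.65 | 0.90 |

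**3. The criterion as a demonstration that the true rate exceeds 80%.** Exact binomial test of 0.80, upper tail 0.025.

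- n=40: 38 detections needed; power 0.223 at 0.90 and 0.993 at 0.99.
- n=22: all 22 needed; power 0.098 at 0.90 and 0.802 at 0.99.
- n=12 and n=10: rejection is impossible, since 0.8^12 = 0.069 and 0.8^10 = 0.107.

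**4. Precision (exact 95% intervals).** 33/40: 67–93%. 36/40: 76–97%. 18/22: 60–95%. 20/22: 71–99%.

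**5. Pooled against per-pattern HIIT reading.** Passing both patterns needs at least 10 + 9 = 19 detections, which always passes the pooled rule. The chance that the readings disagree is therefore the difference of the two probabilities. At 0.90 it is 0.938 − 0.655 = 0.283; at 0.95, 0.996 − 0.896 = 0.100; at 0.99, about 1.000 − 0.996 = 0.004.

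**The case against.** The strongest reply is that this is a pilot. Section 7.2 makes description primary and sets a point-estimate rule, not a test against 0.80. On that rule, 40 patients or a pooled 22 pass with probability 0.96 or 0.94 at the plan's own alternative of 0.9. This stands. A reader might infer from the 22% and 10% that the study is underpowered or should be enlarged. The documents do not support that, because they plan no such test, and at 0.99 the same test has 99% and 80% power. What remains is that section 7.1 itself claims power, with no calculation that bears on the rule.

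A reader might also infer that the prevalence-range claim is false. If the number of positives is random, power at prevalence 0.1 is 1 − (1 − 0.1 × 0.9)^20 = 0.848. That needs n=20 and one observation per subject. With 40 subjects the same formula gives 1 − 0.91^40 = 0.977. Section 7.1 does not say what unit prevalence refers to, and sections 5.5 and 5.6 describe continuous badge data and walks on up to three days. The claim should not be called wrong.

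Finally, the plainer reading of the HIIT criterion is one proportion over assigned badges, and the two readings nearly coincide at rates close to 100%. That also stands. However, section 7.1 itself warns that badge positioning may lower performance, so 0.90 cannot be set aside.

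**Conclusion.** The point holds, with limits. The calculation in section 7.1 is arithmetically sound but answers a different question from the >80% criterion. The three power assertions for 40, 50 and 22 participants rest on nothing else, and the provider assertion has no criterion to refer to.

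Meeting the criterion is a usable descriptive result. It does not by itself show a true rate above 80%, because at a true rate of exactly 80% it would still be met 44% (n=40) or 54% (n=22, pooled) of the time. These figures assume independent results, one per patient, and full evaluability.

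For the closed 40-patient cohort this is minor. For HIIT it is worth correcting now, because the choice between readings would change the conclusion in about 28% of trials at a true rate of 0.90. That share falls to about 10% at 0.95 and under 1% at 0.99. The documents do not show that the sample sizes are wrong or that a per-pattern criterion was intended.

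**What to change.** In section 7.1:

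- Keep the n=20 calculation as a record of how the sample was set, and say that its null of 0 does not bear on the >80% criterion. Leave the prevalence-range sentence alone.
- Replace the power sentence for the 40 patients with precision, marked as retrospective because the cohort is closed: exact 95% interval 67–93% at 33/40, the smallest passing count, and 76–97% at 36/40.
- Replace the HIIT power sentence with pooled precision: 60–95% at 18/22 and 71–99% at 20/22, recomputed if fewer than the maximum of 22 enrol.
- Remove the provider power sentence and rest the maximum of 50 on availability, which the section already describes.
- Add that meeting the criterion is descriptive and does not by itself show a true rate above 80%.

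In section 7.2, before HIIT data are analysed, state that the criterion is pooled over assigned badges. Report the continuous (12) and interval (10) groups separately, each with its exact interval.

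The cost is a few reworded sentences and a less favourable stated justification. Enrolment, data collection and the 80% threshold are unchanged.
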